Hyp. 1.a. The benefit of ACT+CM over DC+CM on initial response (abstinence) rates will be greater in the subgroup of individuals with higher pretreatment EA scores. Adding the interaction term (EA-by treatment) to the logistic regression model will evaluate the moderating effect of EA.

Hyp. 1.b. ACT+CM effects on initial treatment response will be mediated by the primary hypothesized treatment mechanisms, EA and reward sensitivity. In the context of the direct effect of treatment on response, mediational modeling will evaluate the *indirect* effect of treatment on response via EA and reward sensitivity variables, using the product moment method with bootstrapped 95% CI and Bayesian posterior distributions.

Hyp. 2. For initial non-responders, continued ACT+CM treatment with pharmacotherapy (modafinil) augmentation will be most effective in promoting abstinence relative to treatment combinations involving DC and/or placebo. Logistic regression will evaluate cocaine abstinence at the end of second treatment in a set of contrasts: (1) modafinil versus placebo within each initial treatment; (2) the sequence of ACT+CM with modafinil augmentation versus DC+CM with modafinil augmentation.

Hyp. 3. For initial responders, continued ACT+CM will be more effective (higher abstinence rates; < 46% relapse rate) than continued DC+CM. Logistic regression will evaluate cocaine abstinence/relapse at end of second treatment as a function of initial treatment (ACT+CM vs DC+CM).

Power. Power estimates for Hypotheses 1, 2 and 3 will use as the primary outcome (i.e., “response”), two consecutive weeks of cocaine abstinence (BE ≤ 150 ng/mL). Initial treatment response (abstinence) rates are expected to be $\sim 40\%$, based on our previous study¹² and pooled data across cocaine clinical trials⁸⁵; however we predict a difference in response rates, favoring ACT+CM over DC+CM by about 20%, constituting a clinically meaningful treatment effect. Among initial non responders, we expect at least a

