small treatment effect favoring augmentation with modafinil, based on our previous trials.^{29, 31, 32, 43} Among initial responders, we previously observed that approximately 54% remain abstinent (46% "relapse") over an extended period of treatment, up to 12 weeks. Using this estimate for the control group (DC+CM), we predict a difference in response rates, favoring continued ACT+CM by about 15%, translating into a relapse rate of about 30%. Importantly, these effect size estimates are derived from data in which missing data is counted as non-abstinence, which mirrors the way we will be treating missing data for our primary analyses.

Finally, given the uncertainty inherent in pre-existing empirical evidence and even greater uncertainty for conditional probabilities of response, prudence dictated that robust trial planning rely upon probability distributions of plausible effects that take into account the uncertainty of our predictions of effect, rather than simple point-estimates. Adoption of distributional specification of effect sizes and their associated uncertainty required implementation of a Bayesian statistical approach.

Data Simulation Model. Using the above outcome estimates, we conducted a Monte Carlo simulation study to determine predicted power for the planned analyses, taking into account uncertainty in parameter estimates. **Figure B.3.2.x** depicts the trial design with probability point-estimates and 95% Credible Limits for each treatment cell, derived from logistic regression models with vague neutral priors, averaged across $K = 500$ simulations. *Simulated results for anticipated cell sizes are shown in italics.* **Table B.3.2.x** displays estimates of power to detect any benefit ($H_A: \theta > 0$) conferred by the treatment hypothesized as being superior. All primary hypotheses demonstrate a > 80% chance of detecting 0.90 probability of benefit for a sample of $N = 160$. Also shown in **Table B.3.2.x** are the point-estimates and 95% Credible Intervals of specified effects averaging over the $K = 500$ simulations.

Summary. Using data-driven effect sizes that take into account uncertainty, simulation results indicate that with a sample size $N=160$, we have roughly 80% power for all primary hypotheses. Further, we stipulate *a priori* that a > 80% chance of treatment conferring benefit (i.e. $Pr(\Pr \theta > 0 | \text{data}) > 0.80$)

[figure not shown]

Table B.3.2.x.

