Effect	Posterior Probability $Pr(\theta > 0)$	Power to Detect $Pr(\theta > 0)$	Average Point Estimate	Average Interval (95% C.I.) Estimate
Effect of Initial Treatment Hypothesis Test Aim 1: Contrast 1 vs 2*	0.90	0.83	0.20	0.05-0.34
Effect of Second Treatment (Initial non-responders) Hypothesis Test Aim 2				
Contrast 5 vs 6*	0.80	0.81	0.17	0.06-0.27
Contrast 7 vs 8*	0.80	0.81	0.13	0.05-0.21
Contrast 6 vs 8*	0.85	0.80	0.16	0.07-0.25
Effect of Second Treatment (Initial responders) Hypothesis Test Aim 3:				
Contrast 3 vs 4*	0.85	0.80	0.16	0.07-0.25

*Contrast numbers correspond to numbers in black boxes on Figure B.3.2.x.

constitutes sufficient evidence for results from this Stage II project to support a “Go” decision to advance to Phase III confirmatory studies.

Protection of Human Subjects

Selection Criteria

Eligible participants will:

1. be between 18 and 60 years of age
2. meet DSM-5 criteria for current cocaine use disorder of at least moderate severity (≥ 4 symptoms)
3. have at least 1 positive urine BE specimen (≥ 150 ng/mL) during intake
4. be in acceptable health on the basis of interview, medical history and physical exam
5. agree to use an acceptable method of birth control during study participation and for one month after discontinuation of the study medication. Non-hormonal methods of contraception are recommended, including barrier contraceptives (e.g., diaphragm, cervical cap, male condom) or intrauterine device (IUD). Steroid contraceptives if used with non-hormonal methods are acceptable.
6. be able to understand the consent form and provide written informed consent
7. be able to provide the names of at least 2 persons who can generally locate their whereabouts.

Exclusion criteria include:

8. current DSM-5 diagnosis for substance use disorder (of at least moderate severity) other than cocaine, marijuana, alcohol, or nicotine
9. current alcohol use that meets for physiological dependence requiring detoxification or makes participation medically unsafe as determined by the medical director.
10. have a DSM-5 axis I psychiatric disorder or neurological disease or disorder requiring ongoing treatment and/or making study participation unsafe (e.g., psychosis, dementia).
11. significant current suicidal or homicidal ideation
12. medical conditions contraindicating modafinil pharmacotherapy (e.g., major cardiovascular disease, severe liver disease based on Child-Pugh score of B or C, serious kidney problems)

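### Table B.3.2.x overstates Aim 3 power (about 0.56 to 0.66, not 0.80) and gives Aim 2 and Aim 3 intervals that 160 patients cannot produce

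*Combined protocol and SAP*

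**What the plan says.** The Power section expects about 40% initial response, with a difference "favoring ACT+CM over DC+CM by about 20%, constituting a clinically meaningful treatment effect". Among initial responders it takes 54% remaining abstinent under DC+CM and a difference "favoring continued ACT+CM by about 15%, translating into a relapse rate of about 30" percent. True effects were not held fixed; planning used "probability distributions of plausible effects that take into account the uncertainty of our predictions of effect".

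Table B.3.2.x then gives, for each contrast, a posterior-probability threshold, power, average effect and average 95% interval over 500 simulations. The Aim 3 row is "Contrast 3 vs 4* 0.85 0.80 0.16 0.07-0.25" and the first Aim 2 row is "Contrast 5 vs 6* 0.80 0.81 0.17 0.06-0.27". The other Aim 2 rows are 7 vs 8 (0.80, 0.81, 0.13, 0.05-0.21) and 6 vs 8 (0.85, 0.80, 0.16, 0.07-0.25). Hyp. 2 lists modafinil against placebo within each initial arm, plus "the sequence of ACT+CM with modafinil augmentation versus DC+CM with modafinil augmentation".

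The Summary concludes that "we have roughly 80% power for all primary hypotheses", and sets "a > 80% chance of treatment conferring benefit" as sufficient for a Go decision. Aims and Hypotheses lists Aims 2 and 3 as secondary.

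**The concern.** Aims 2 and 3 are tested in subsets. Only responders enter Aim 3, and each Aim 2 cell is about half of one arm's non-responders. Yet the printed intervals for these small groups (half-widths 0.08 to 0.105) are narrower than the Aim 1 interval of 0.05 to 0.34, which uses all 160 patients. Rows 6 vs 8 and 3 vs 4 also agree in every column, although they concern different patients.

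The table tells readers that the second-stage contrasts have about 80% power and intervals clear of zero. If that is wrong, an inconclusive second-stage result could be read as evidence against benefit when the trial was simply too small to show it.

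**Working it through.** **Method.** SE = sqrt(p1·q1/n1 + p0·q0/n0), with q = 1 - p. With vague priors, power to exceed posterior probability t is about Φ(d/SE - z_t), where z = 0.842, 1.036 and 1.282 for t = 0.80, 0.85 and 0.90. The half-width is 1.96·SE.

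**Calibration on Aim 1.** 60% vs 40%, 80 per arm (1:1 assumed; no ratio is stated). SE = sqrt(0.24/80 + 0.24/80) = 0.0775. The interval is 0.05 to 0.35 (printed 0.05-0.34). Power at 0.90 is Φ(2.582 - 1.282) = 0.90 (printed 0.83). The method reproduces the interval and is generous on power.

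**Aim 3 cell sizes.** 60% vs 40% response gives 48 and 32 responders; 50% vs 30% gives 40 and 24.

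| ACT vs DC abstinence | n | SE | Power at 0.80 | at 0.85 | at 0.90 |
|---|---|---|---|---|---|
| 0.70 vs 0.54 | 48/32 | 0.1102 | 0.729 | 0.661 | 0.568 |
| 0.70 vs 0.54 | 40/24 | 0.1249 | 0.670 | 0.597 | 0.500 |
| 0.69 vs 0.54 | 48/32 | 0.1105 | 0.697 | 0.626 | 0.530 |
| 0.69 vs 0.54 | 40/24 | 0.1253 | 0.639 | 0.564 | 0.466 |

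Monte Carlo with random responder counts and Beta(1,1) posteriors gives about 0.57 to 0.67 at 0.85. Power of 0.80 at that threshold needs (p1·q1 + p0·q0)·((1.036 + 0.842)/d)² per arm, that is 64 (d = 0.16) to 73 (d = 0.15) responders.

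**Aim 3 interval, 0.70 vs 0.54.** 0.16 ± 0.216 = -0.06 to 0.38 (48/32); 0.16 ± 0.245 = -0.09 to 0.41 (40/24). A half-width of 0.09 needs (0.2100 + 0.2484)/(0.09/1.96)² = 217 responders per arm. If all 160 patients responded, it would still be 0.148.

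**Uncertain effects.** If the true effect has standard deviation s, power is about Φ((d - z·SE)/sqrt(SE² + s²)). Taking s = 0.07 brings Aim 1 to 0.83, as printed. The same s gives Aim 3 0.56 to 0.64 at 0.85.

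**Aim 2 intervals, best case.** With 0% abstinence in the comparator the variance is smallest, and n per cell = d(1 - d)/(half-width/1.96)². No cell can exceed 40 (half of 80, if nobody responds).

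| Contrast | d | Printed half-width | n per cell needed | Half-width at n = 40 |
|---|---|---|---|---|
| 5 vs 6 | 0.17 | 0.105 | 49.2 | 0.116 |
| 7 vs 8 | 0.13 | 0.08 | 67.9 | 0.104 |
| 6 vs 8 | 0.16 | 0.09 | 63.7 | 0.114 |

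With 1:1 re-randomisation, the stated response rates give 16 to 20 per ACT cell and 24 to 28 per DC cell.

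**Aim 2 power, conditional.** The cell rates are in a figure not shown, but the table's effects are linked. If 6 vs 8 is the comparison of the two modafinil cells, ACT+placebo exceeds DC+placebo by 0.13 + 0.16 - 0.17 = 0.12. The comparator in 5 vs 6 is then at least about 12%. For an illustrative DC+placebo abstinence of 0 to 30%:

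- 5 vs 6: power 0.55-0.70 at 0.80 (printed 0.81), half-width 0.25-0.34. The best case is 0.29 vs 0.12 with 20 per cell: SE 0.1248, power 0.70.
- 6 vs 8: power 0.49-0.62 at 0.85 (printed 0.80), half-width 0.24-0.31.
- 7 vs 8: power at 0.80 is 0.82-0.86 if DC+placebo abstinence is 1%, 0.77-0.80 at 3%, and 0.54-0.76 from 5 to 30%; half-width 0.13-0.27 over the whole range (printed 0.08).

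If the boxes are numbered differently, ACT+placebo is still 0.16 to 0.20 above DC+placebo, and the modafinil row within the ACT arm has power of at most 0.67.

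**Within-row check.** At a fixed effect, 0.16 with half-width 0.09 implies power Φ(0.16·1.96/0.09 - 1.036) = 0.99, not 0.80.

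**The case against.** The strongest reply is that Figure B.3.2.x, not available here, holds the cell rates and sizes, so the Aim 2 power figures rest on assumptions. That stands for Aim 2 power: the ranges above are illustrative, and 7 vs 8 may be correct if DC+placebo abstinence is very low. It does not touch the intervals, which fail at every comparator rate and at the largest possible cell size, or Aim 3 power, whose inputs are in the text.

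A second reply is that the Aim 2 and 3 intervals may be one standard error either side, mislabelled as 95%. The rows would then imply power of 0.77 to 0.78, close to the table. This is plausible, but the labels would still be wrong, and Aim 3 would still need 0.4584/0.09² = about 57 responders per arm against 24 to 48.

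Third, the effect standard deviation of 0.07 is fitted here, and the plan speaks of greater uncertainty for the conditional response rates. A larger value would not bring Aim 3 up to 0.80.

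Fourth, Aims 2 and 3 are secondary and the Go rule names no contrast. Both are true. Aim 1 exceeds 0.80 with probability about 0.96 by the same formula, so a shortfall in Aim 3 is not a failure of the whole trial. The Power section nevertheless covers Hypotheses 1, 2 and 3, and the table prints figures for all of them. Last, the identical rows are a query, not a proven error.

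**Conclusion.** The table is wrong as written. Aim 3 power at its 0.85 threshold is 0.56 to 0.66, not 0.80. At the 0.80 Go threshold it is 0.64 to 0.73, so a real Aim 3 benefit of the planned size would miss that threshold 27 to 36% of the time, where the table implies less than 20%. The Aim 3 interval and all three Aim 2 intervals cannot arise from 160 patients. At the expected cell sizes the 3 vs 4 interval includes zero and, under the linked rates, so do those for 5 vs 6 and 6 vs 8.

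This rests on 1:1 allocation at both stages and initial response of 60/40 or 50/30. The statements on 5 vs 6 and 6 vs 8 also rest on the rounded, linked estimates. The error lies in stated power and precision for the secondary aims; the Aim 1 sample size is unaffected.

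**What to change.** - Rerun the simulation with the actual second-stage cell sizes. Replace the Aim 3 power, every Aim 2 and Aim 3 interval, and Aim 2 power where it changes.
- Confirm that the interval column is a 95% interval, and check why rows 6 vs 8 and 3 vs 4 are identical.
- Put the assumed abstinence rate and n for cells 3 to 8 beside the table, in agreement with Figure B.3.2.x, which may already carry them.
- Limit the two general power statements (in Data Simulation Model and Summary) to Aim 1 unless the rerun supports more, and say which aims the word primary covers there.
- Report power at the 0.80 Go threshold alongside any other threshold used.

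The cost is one rerun, one corrected table and two reworded sentences, with no extra patients. The stated power and precision for the secondary aims will look less favourable.
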